SID	Secondary Immunodeficiencies
SmPC	Summary of Product Characteristics
TNBP	

1 INTRODUCTION**1.1 BACKGROUND**

Since more than six decades immunoglobulins have been used to provide antibodies for the prevention of viral and bacterial diseases (replacement therapy) in immunocompromised patients. In the earlier years (around 1950), the IgG preparations were administered intramuscularly. This route of administration causes substantial discomfort, and restricts the amount of IgG that can be given to the patients. Since its use as a replacement therapy for patients with primary (PID) and secondary (SID) immunodeficiencies, the clinical use of intravenous immunoglobulin (IVIG) has expanded and has become an important treatment option in a wide spectrum of diseases. IVIG is used routinely in autoimmune and acute inflammatory conditions due to IVIG's immune-modulatory and anti-inflammatory properties. During the last 25 years, the use of subcutaneously administered immunoglobulins (SCIG) has further contributed to the successful treatment of PID and SID patients. Administration via the SC route offers several advantages over IV infusion from a patient's and a physician's perspective and therefore became an alternative treatment option to IV treatment. After introduction of small, portable syringe drivers, SCIG products have gained even more popularity in Europe, USA, and Canada as a practical, effective and safe treatment, as they can be safely self-administered at home or even when travelling.

octagam® 5% and octagam® 10% are liquid polyvalent IVIG preparations, which are subject to a three-stage viral inactivation. The products are prepared from human plasma and mainly contain human normal immunoglobulin G. The molecules are present in their native form which is essential for the biological activity. octagam® 5%, has been approved in 83 countries worldwide since 1995; octagam® 10% has been approved in 58 countries worldwide since 2008.

octagam® is produced from a pool of at least 3,500 donations of human fresh frozen plasma per batch.¹ The large donor pool ensures that the product contains a broad range of antibodies directed against pathogens and foreign antigens, which is far more diverse than that of plasma from an individual donor. Donor plasma sampling, the manufacturing of the product and the measures to ensure the product's viral safety are subject to strict regulations laid down by regulatory authorities. Octapharma exclusively uses plasma that has been tested by nucleic acid testing (NAT) techniques. The production process contains three validated virus inactivation steps (modified ethanol fractionation, pH treatment, and solvent/detergent (S/D) virus inactivation).

panzyga® (Immune Globulin Intravenous (Human), 10%) is a sterile liquid preparation of highly purified immunoglobulin G (IgG) derived from large pools of human plasma. The panzyga® manufacturing process achieves a significant viral reduction through a combination of two dedicated manufacturing process steps: S/D treatment and nanofiltration (20 nm). The Source Q chromatography (ion-exchange chromatography) step in the panzyga® process also contributes significantly to the viral safety of panzyga®. The efficacy of the virus inactivation procedures has been extensively validated. panzyga® has been approved in 29 countries worldwide since 2016.

cutaquig® is a sterile solution of human normal immunoglobulin containing 16.5% (165 mg/mL) protein for SC administration, prepared from at least 3500 donations of human fresh-frozen plasma. Effective viral reduction is obtained via a combination of 3 validated manufacturing steps: cold-ethanol fractionation, S/D treatment with TNBP (Tri-n-butyl phosphate) and Octoxynol, and pH 4 treatment. cutaquig® has been approved in Canada.

This post-marketing surveillance study is designed to ensure long-term consistency between data from the pre-licensure clinical studies and clinical use. Documentation of the administration of Octapharma's IVIG products (octagam®, panzyga®) and the newly licensed SCIG product (cutaquig®) in clinical practice will not only improve the efficacy and tolerability knowledge database, but will produce findings that cannot be obtained in the same way in controlled clinical studies. This surveillance study will support the optimal use of octagam®, panzyga®, and cutaquig®, thus bringing benefit for both physicians and patients.

2 OBJECTIVES

- 1) The primary objective is to document the safety and tolerability of octagam®, panzyga® and cutaquig® in any indication, age group or treatment regimen.
- 2) The secondary objective is to document their efficacy in patients receiving treatment.

¹ For simplicity, the term octagam® refers in this document, to both strengths (5% and 10%) unless noted otherwise.

3 INVESTIGATIONAL PLAN

3.1 OVERALL DESIGN AND PLAN

This is a prospective, multicentre, non-interventional study (NIS).

The treating physician decides whether, how and for how long a patient is to be treated with octagam®, panzyga®, and/or cutaquin®.

3.1.1 Population

octagam®, panzyga®, and/or cutaquin® will be prescribed regularly to any patient who needs to be treated with an IgG product because of their medical condition and whom the treating physician wants to include in this observational study, after the decision has been made to prescribe IVIG or SCIG treatment.

This study will observe 300–500 patients treated with octagam®, panzyga® and/or cutaquin® in any indication, age group, gender or treatment regimen. It is not possible to specify the exact number of doses per patient that are to be documented because of the different indications for use.

All patients who are eligible to enter the study will be informed by the physician before study entry about the conduct, implication and goal of this Post-Authorisation safety Surveillance. This will be done following center internal procedures. Each patient is uniquely identified in the study by an ID number that will be provided by the study centre to ensure patient confidentiality. Once assigned to a patient, a patient number will not be reused nor will the patient be allowed to re-enter the study after completion or discontinuation.

3.1.2 Centres

This observational study is conducted in outpatient and inpatient centres globally.

3.1.3 Flowchart of Study Events

Due to its non-interventional and observational nature, this study will strictly exclude pre-defined visits or time schedules (except that a close-out visit should take place before a patient leaves the NIS). However, it is recommended to perform subsequent visits on regular intervals according to standard treatment procedures for the respective disease.

Table 1 lists all assessments recommended by this protocol.

Table 1: Assessment schedule

Assessments	Baseline or Entry Visit	Subsequent Infusion Visits	Close-Out Visit
Baseline assessments	✓		
Previous IVIG and SCIG treatments	✓		
Concomitant medication(s)	✓	✓	✓

octagam®/panzyga® /cutaquig® treatment details		✓ ¹	
Information on efficacy		✓	✓
Adverse drug reactions (ADRs)		✓ ¹	✓
Checking of patient diary for patients doing cutaquinig® home treatment		✓	✓

¹ May take place at the same day as baseline/entry visit.

Data obtained during the study will be recorded, for this purpose Electronic case report forms (eCRF), namely a secure web-based data entry system (see Section 7.1), will be used.

The eCRF will consist of 4 main sections:

- 1) Baseline documentation: Must be completed when a new patient is enrolled. The patient's demographic data (year of birth or age, gender, weight, general condition, risk factors), medical history, basic disease (including date of diagnosis and details on previous treatments), and concomitant medications and diseases are to be documented.
- 2) Treatment record: Treatment details with octagam®/panzyga®/cutaquig® are to be documented, including date of administration, method of administration, infusion speed, dosage, batch number, concomitant medications incl. treatment details, if applicable. In case of home treatment with cutaquinig®, patients will be asked to fill in a study diary to carefully document information (ie. including date and method of administration, infusion speed, dosage, batch number; concomitant medications incl. treatment details, if applicable).
- 3) Suspected ADRs occurring during or after administration of octagam®/panzyga®/cutaquig® are to be recorded on separate ADR forms. Patients are to be advised to document in their diaries every ADR they experience at home, also in case they do not need any medical treatment.
- 4) Efficacy assessment: Available efficacy data are to be documented.

3.1.4 Study Duration

This study started in August 2011 in 4 European countries and was then extended to Canada. The European centres are now closed or being closed and the study will continue in Canada. Planned study end is 2022.

The duration of observation for an individual patient will be as long as any of the described IVIGs or the SCIG will be prescribed by the treating physician and until the next regularly scheduled visit of the patient after last infusion. For patients with PID or SID the observation period should last at least 12 months, if possible.

3.1.5 Premature Termination

If, for any reason, the physician or the patient decides to discontinue treatment with octagam®, panzyga® or cutaquinig®, the observation period of this patient is to be

terminated and a close-out visit should take place. The physician should make efforts to complete and document all available observations. The reason for termination is to be documented.

If the reason for discontinuing octagam®, panzyga® or cutaqui® therapy is the occurrence of an ADR, the specific reaction must be recorded and the outcome is to be documented.

4 TREATMENT

4.1 OBSERVATIONAL DRUGS

Subjects documented in this NIS will receive commercially available octagam®, panzyga® or cutaqui® prescribed by a physician.

octagam® 5% contains 50 mg protein per mL of solution of which $\geq 95\%$ is IgG; the IgA content is ≤ 0.2 mg/mL and IgM content is ≤ 0.1 mg/mL. octagam® 10% contains 100 mg protein per mL of solution of which $\geq 95\%$ is IgG; the IgA content is ≤ 0.4 mg/mL and IgM content is ≤ 0.3 mg/mL. All four IgG subclasses are present in proportions corresponding to the normal physiological distribution. The product is liquid, contains maltose and has undergone multiple virus inactivation procedures.

panzyga® is a 10% solution ready for intravenous administration. panzyga® is made from a pool of at least 1000 donations of human fresh-frozen plasma per batch. During the manufacturing process of panzyga®, significant viral reduction is obtained via a combination of different validated steps during the manufacturing process. The efficacy of the virus inactivation procedures has been extensively validated according to relevant international guidelines in place.

cutaqui® is a sterile solution of human normal immunoglobulin containing 16.5% (165 mg/mL) protein, prepared from at least 3,500 donations of human fresh-frozen plasma per batch. Effective viral reduction is obtained via a combination of three validated manufacturing steps. The manufacture of cutaqui® is based on the octagam® manufacturing process including an additional adsorption step onto a commercially available and widely used chromatography column for the removal of coagulation factor XI (FXI). The process is identical up to the step of diafiltration.

octagam® 5% can be stored for 2 years at a temperature of +2 °C to +25 °C. octagam® 10% can be kept refrigerated at +2 °C to +8 °C for 2 years but can also alternatively be stored for 9 months at room temperature, in which case the end date automatically becomes the expiry date. panzyga® can be stored at +2 °C to +8 °C for 24 months from the date of manufacture. Within this shelf-life the product may be stored up to 9 months at ≤ 25 °C. After the storage at ≤ 25 °C the product must be used or discarded. cutaqui® can be stored for 2 years at +2 °C to +8 °C. Within this shelf-life the product may be stored up to 6 months at ≤ 25 °C and must be used or discarded within that period.

Patients are treated with octagam®, panzyga® or cutaqui® according to the Investigator's prescription. For dosage recommendations please refer to the local octagam®, panzyga® or cutaqui® package leaflets.

Dosage and duration of treatment is at the sole discretion of the Investigator and will depend on the type and/or severity of the disease and the patient's clinical condition.

In case of SCIG home treatment the Investigator should promote compliance by instructing the patient to take cutaqui[®] exactly as prescribed and by stating that compliance is necessary for the patient's safety. The patient should be instructed to contact the Investigator if he/she is unable for any reason to administer cutaqui[®] as prescribed.

All dosages of octagam[®], panzyga[®] or cutaqui[®] that a patient received during the observation period at the study center are to be recorded on the corresponding eCRF pages. Dosages of cutaqui[®] that a patient administered during the observation period at home are to be recorded in the patient diary and will be entered into the eCRF later. It is of utter importance that all data entered into the diary are checked by the Investigator for completeness and any safety-relevant issues (including infusion site reactions) during each patient's visit to the study center.

Any drug dose adjustment and interruptions should be recorded on the corresponding eCRF page.

If, for any reason, the Investigator or the patient decide to discontinue the treatment with octagam[®], panzyga[®] or cutaqui[®], the observation period of this patient will be terminated. Efforts should be made to arrange a close-out visit. The reason(s) for termination in the eCRF is to be documented. Switching from one Octapharma Ig product to another Octapharma Ig product is possible without termination of the study but should be documented.

4.2 CONCOMITANT TREATMENTS

Any other concomitant treatments are at the Investigator's discretion and need to be documented in the eCRF or the patient diary and transferred later into the eCRF.

The Investigator should instruct the patient to notify the site about any new medications he/she takes after starting this observation.

5 SAFETY MONITORING

To allow continuous monitoring of the product safety all adverse drug reactions (ADRs) and other safety-relevant information as defined below are to be documented.

5.1 ADVERSE DRUG REACTION

An ADR is any noxious and unintended response to the study drug which occurs at doses normally used in humans for the prophylaxis or therapy of disease or for the restoration, correction or modification of physiological function. Response in this context means that a causal relationship between the study drug and an adverse event (AE) is at least a reasonable possibility.

Serious ADR

A serious ADR is any untoward medical occurrence that is considered related to study drug and that at any dose:

- is resulting in death;

- is life-threatening ("life-threatening" means that the patient was at an immediate risk of death at the time of the event; it does not mean a hypothetical situation of what could or would have happened if, for example, no treatment had been administered);
- requiring hospitalisation or prolongation of existing hospitalisation (hospitalisation does not refer to the treatment of an ADR on an out-patient status);
- resulting in persistent or significant disability/incapacity;
- is a congenital anomaly/birth defect;
- is any other important medical event (e.g. suspected transmission of an infectious agent, or other reactions that should be reported in an expedited manner although they did not immediately result in one of the above seriousness criteria).

Medical judgment should be exercised in deciding whether an ADR is serious in other situations: Important ADRs that are not immediately life-threatening or do not result in death or hospitalization but may jeopardize the patient or may require intervention to prevent one of the other outcomes listed in the definitions above, should also be considered serious.

Causality assessment of cases should follow the WHO-UMC causality categories: <https://www.who-umc.org/media/2768/standardised-case-causality-assessment.pdf>

5.2 OTHER RELEVANT DRUG SAFETY INFORMATION

The following events should also be reported:

- a) pregnancies/breastfeeding;
- b) drug abuse (persistent or sporadic, intentional excessive use of a medicinal product, which is accompanied by harmful physical or psychological effects), misuse;
- c) overdose (treatment exceeding the medically recommended dose);
- d) medication errors (prescribing or dispensing error);
- e) interaction(s) with other medicinal product or device;
- f) suspected transmission of infectious agent;
- g) off-label use;
- h) occupational exposure;
- i) lack of efficacy;
- j) quality complaints with harm (or potential harm) of the patient.

This information should be reported if associated with the use of octagam®, panzyga® and/or cutaqui® or – in case of pregnancy/breastfeeding – if observed during treatment with octagam®, panzyga® and/or cutaqui®.

Above mentioned events should also be recorded if no ADR occurred.

In the eCRF specific pages are included for data entry for ADRs and infusions site reactions.

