5.3 REPORTING OF ADRS AND OTHER SAFETY INFORMATION

All ADRs and other safety information as defined above have to be documented on the specific electronic forms of the electronic data capturing (EDC) system.

Serious ADRs have to be entered *immediately* (within 24 hours) into the eCRF and should be transferred electronically to Octapharma.

Non-serious ADRs and other safety information should be reported upon recognition but no later than 10 days.

Patients undergoing home treatment should be asked to inform their treating physician immediately of any ADR, or other relevant safety information. The treating physician will assess the causal relationship for ADR and report the event as described above.

Octapharma will handle all ADRs as post-marketing safety reports and will report the cases in compliance with applicable regulations for pharmacovigilance.

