6 STATISTICAL CONSIDERATIONS

Statistical analysis of all parameters will be descriptive. SAS software will be used for the statistical analysis. All data will be listed in their entirety and will be presented in summary tables.

In general, all study parameters will be described using the following standard statistical parameters: arithmetic means, standard deviation, median, minimum and maximum. Frequency tables (absolute and relative frequencies) will be produced for categorical parameters.

The demographic data, indications for use, baseline values, and number of doses will be summarised descriptively. Tolerability and efficacy assessments made by the treating physicians will be presented by frequency tables and corresponding figures.

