### 6.2 Handling of missing data and outliers

#### 6.2.1 Missing data analysis methods

For the handling of missing numbers of infections, see sections 7.3.2 and 7.5.2. Missing values of body weight in the calculation of measures of exposure will be handled as described in section 7.4.2. Otherwise, missing data will not be imputed for any analysis. For the handling of missing or incomplete start and end dates of Individual Case Safety Reports and medications, see section 6.2.2.

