### 7.5.2 Analysis of efficacy endpoint(s)

#### For patients with diagnosis PID or SID:

For each fourth infusion visit (starting with infusion visit 4) and the close-out visit the influence of the treatment with IVIG/SCIG on the frequency, intensity and duration of infections and the consumption of antibiotics since the last visit is recorded. Possible outcomes are beneficial, unchanged and unfavorable. Counts and percentages of these outcomes will be summarized by infusion visit and for the close-out visit by treatment group and overall in the Safety population. In addition, the patient's last available assessments will be summarized. These summaries will be generated for the pool of PID/SID patients and for each of the two diagnoses separately.

For each fourth infusion visit (starting with infusion visit 4) and the close-out visit the occurrence of new infectious episodes (yes/no) since the last visit is recorded. In case of the occurrence of new infectious episodes patients are asked regarding the infected area and the number of infectious episodes in this area using the following pre-specified categories:

- Serious infections of the upper respiratory tract

- Serious infections of the lower respiratory tract
- Urinary tract infections
- Bacteremia/sepsis
- Bacterial meningitis
- Osteomyelitis/septic arthritis
- Bacterial pneumonia
- Visceral abscesses
- Other infectious diseases

The number and percentage of patients with new infectious episodes since the last visit and the number and percentage of patients with new infectious episodes in each of the above categories will be summarized by infusion visit and for the close-out visit by treatment group and overall in the Safety population. In addition, this summary will be generated for the patient's last available assessment.

Further the occurrence of any infectious episodes during the course of the study, the occurrence of any infectious episodes in each of the above categories during the course of the study, the total number of infectious episodes and the total number of infectious episodes in each of the above categories will be summarized by treatment group and overall in the Safety population. These summaries will be generated for the pool of PID/SID patients and for each of the two diagnoses separately.

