### **7.6.4 Other safety assessments**

At the close-out visit patients are asked how the study IVIG/SCIG treatment was tolerated in comparison to previous IVIG/SCIG treatment. The outcome of this survey (Not applicable, good, moderate, bad) will be summarized by counts and percentages by treatment group and overall in the Safety population. This summary will also be generated by diagnosis.

In case of a pregnancy the respective form in the eCRF has to be completed. The entries from the pregnancy form will only be listed.

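### Lack-of-efficacy reports must be documented but feed no SAP table, leaving three places where efficacy can look better than it was

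*Protocol*

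**What the plan says.** **Reporting.** Protocol 5.2 opens its list with "The following events should also be reported" and includes "i) lack of efficacy". It adds that these items are to be recorded even when there was no ADR. The binding wording is in Protocol 5.3: "All ADRs and other safety information as defined above have to be documented on the specific electronic forms", with a 10-day limit for non-serious ADRs and other safety information.

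**Presentation.** Protocol 6 promises: "All data will be listed in their entirety and will be presented in summary tables".

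**Efficacy tables.** SAP 7.5.2 uses ratings and infection counts only.
- PID/SID: "For each fourth infusion visit (starting with infusion visit 4) and the close-out visit the influence of the treatment with IVIG/SCIG" is recorded as beneficial, unchanged or unfavorable, together with new infections. There are by-visit, last-available and whole-study summaries.
- Other diagnoses: disease development is rated at every infusion visit and at close-out, with by-visit and last-available summaries. A second item, the influence of treatment on the course of the disease, is asked at close-out only.

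**Missing ratings.** After treatment stops, Protocol 4.1 says "Efforts should be made to arrange a close-out visit", and Protocol 3.1.5 says the visit should happen. Missing infection counts and body weights have their own rules in the SAP, as do incomplete dates. For everything else, SAP 6.2.1 says "Otherwise, missing data will not be imputed for any analysis".

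**Other Protocol 5.2 items.** Pregnancy is the only one given its own rule in SAP 7.6: "The entries from the pregnancy form will only be listed". SAP 8 declares one change from the protocol, the dropped figures.

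**The concern.** A lack-of-efficacy report is the most direct record of treatment failure that this study requires, and documenting efficacy is its secondary objective. The SAP nevertheless has no table in which such a report would be counted.

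This matters most where the planned ratings are weakest. A patient who stops because the product did not work may not return for close-out. If so, the failure report exists but the rating does not, and the percentages rest on the patients who were rated. If failures go unrated more often than other patients, the favourable share rises. The data needed to see this would already be in the study.

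**Working it through.** The documents state no efficacy rate, missing-data rate, power or calculated sample size, so there is no figure of the plan to reproduce. The check compares the texts and then gives an illustration on assumed inputs.

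**Step 1. Where could a failure be seen?**

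| Display | Shows | Limit |
|---|---|---|
| PID/SID ratings and infections (SAP 7.5.2) | Every fourth infusion visit from visit 4, close-out, last available | No rating before visit 4 unless there is a close-out visit |
| Other diagnoses, disease development (SAP 7.5.2) | Every infusion visit, close-out, last available | Last rating may predate the failure |
| Other diagnoses, treatment influence (SAP 7.5.2) | Close-out only | No fallback |
| Withdrawal reasons (SAP 7.2) | Patients who leave early | Does not show those who continue, or who switch between the sponsor's products, which Protocol 4.1 allows without ending participation |
| Listings (SAP 7.1) | All patient data | Change no percentage |

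Three gaps follow:
1. The treatment-influence table for patients without PID or SID omits anyone without a close-out rating.
2. A PID/SID patient who stops before infusion visit 4 and has no close-out visit contributes no efficacy rating.
3. A last available rating can be older than the failure. This is more likely in PID/SID, where ratings come at every fourth infusion visit.

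SAP 7.5.2 also states no denominator and no missing category, whereas SAP 7.2 and 7.6.1 name theirs.

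**Step 2. Size when unrated patients are dropped (all inputs assumed).** Let f be the true failure share, m the share of failures without a close-out rating, and m0 = 10% the same share among non-failures.

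Apparent non-failure = (1−f)(1−m0) / [(1−f)(1−m0) + f(1−m)]

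For f = 20% and m = 50%: 0.80×0.90 = 0.72; 0.20×0.50 = 0.10; 0.72/0.82 = 87.8%, against a true 80.0%.

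For the last-available table, let a share r of patients without a close-out rating, in both groups, have an earlier rating that shows their status correctly. With r = 0.5: 0.80×(0.90+0.05) = 0.76; 0.20×(0.50+0.25) = 0.15; 0.76/0.91 = 83.5%.

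| f | m | True | Close-out only | Last available, r = 0.5 | r = 0.9 | r = 1 |
|---|---|---|---|---|---|---|
| 5% | 30% | 95.0% | 96.1% | 95.5% | 95.1% | 95.0% |
| 5% | 50% | 95.0% | 97.2% | 96.0% | 95.2% | 95.0% |
| 10% | 30% | 90.0% | 92.0% | 91.0% | 90.2% | 90.0% |
| 10% | 50% | 90.0% | 94.2% | 91.9% | 90.4% | 90.0% |
| 20% | 30% | 80.0% | 83.7% | 81.7% | 80.3% | 80.0% |
| 20% | 50% | 80.0% | 87.8% | 83.5% | 80.7% | 80.0% |

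With equal missingness (m = m0 = 10%) the gap is zero: 0.72/(0.72+0.18) = 80.0%. The percentages do not depend on whether 300 or 500 patients are observed.

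**Step 3. Size when the last rating is too old.** Here the patient is not dropped but counted with a favourable rating. If everyone has some rating, non-failures are rated correctly, and a share q of the failures without close-out carries an older favourable rating, the excess is f×m×q. With m = q = 50%, that is 0.05×0.50×0.50 = 1.25 points at f = 5% and 0.20×0.50×0.50 = 5.0 points at f = 20%.

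**The case against.** The strongest reply is that the plan does look for failure in several ways. Ratings at infusion visits include deteriorated or unfavorable, both patient groups have a last-available summary, infections are counted over the whole study, withdrawal reasons are tabulated, and SAP 7.7.1 repeats summaries by diagnosis. Protocol 5.2 is a safety-reporting list, and Protocol 6 bases efficacy on the treating physicians' assessments, which SAP 7.5.2 implements. Efficacy is secondary, descriptive and untested.

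Most of this stands. A reader might infer that failures without a close-out rating vanish from the analysis, or that failures in continuing patients are shown nowhere. The documents support neither: such a patient leaves the close-out tables but can still appear in the by-visit, last-available, infection and withdrawal displays. A reader might also infer that efficacy is shown to be inflated. It is not; the effect is conditional and every input above is assumed.

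It would also go too far to count unrated patients as unfavorable. No physician gave that rating, and a treatment that did nothing could equally be rated unchanged.

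Two points are open. The eCRF and the table templates are not among the documents; Protocol 5.2 mentions specific pages only for ADRs and infusion site reactions. A lack-of-efficacy report might therefore be entered on an ADR form. Under SAP 7.6.1 it would then be excluded if rated not related (except in the listing of deaths), or otherwise be counted as an ADR in the primary endpoint. The SAP addresses neither case, which is a reason to state a rule.

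The reply does not answer the undeclared departure from Protocol 6 or close the three gaps. The listings in SAP 7.1 meet the listing half of the promise, not the summary-table half.

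**Conclusion.** The point holds in limited form. Lack-of-efficacy reports must be documented, the protocol promises summary tables of all data, no SAP table uses the reports, and SAP 8 does not say so. That rests on the text alone.

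The effect on efficacy is a possibility confined to the three gaps. In tables that drop unrated patients, it arises only if failures miss ratings more often than others. In the last-available tables, it also needs an earlier rating to be absent or to predate the failure.

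The documents give no size. On the assumptions shown, with 30% to 50% of failures and 10% of non-failures unrated, close-out-only tables gain 1.1 to 7.8 points. At 50%, the last-available tables gain 1.0 to 3.5 points at r = 0.5 and nothing at r = 1; older favourable ratings could add to this. The change is worth making because it is cheap and lets readers judge the condition for themselves, but it does not affect the primary ADR analysis unless such reports are coded as ADRs.

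**What to change.** **SAP 7.5.2**
- Tabulate, by product and diagnosis, the number and percentage of patients with a lack-of-efficacy report or termination for lack of efficacy, and how many of them have no close-out rating or no efficacy rating at all.
- State the denominator and show a missing row in the efficacy tables.
- Add a supportive close-out table in which such patients without a close-out rating count as not beneficial.

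**SAP 7.6.4**
- Count and list the other Protocol 5.2 items by product.
- State that lack-of-efficacy reports entered on an ADR form are reported separately from ADRs and are not removed by the exclusion of cases rated not related.

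If the sponsor prefers not to tabulate these items, SAP 8 should declare that as a change from Protocol 6.

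**Cost.** SAP wording and a few extra outputs, with no protocol change. How the reports are stored in the eCRF needs confirming first. The descriptive efficacy figure may turn out slightly less favourable.
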